A recent study suggests that patients with functional dyspepsia have low-grade mucosal inflammation, abnormalities of cell-to-cell adhesion proteins which predispose to increased epithelial permeability, and a leaky epithelial barrier¹⁶. Type 1 DM is associated with increased small intestinal permeability even in subjects who do not have celiac disease^{17,18}. Moreover, a comparison of 339 type 1 DM patients and 89 first degree relatives observed higher serum zonulin levels in type 1 DM patients than controls or relatives; patients with increased zonulin had increased epithelial permeability¹⁹. The only study which evaluated small intestinal permeability in type 2 DM used suboptimal techniques and reported normal permeability²⁰.

Our *overall hypothesis* is that intestinal chemosensitivity related to increased epithelial permeability and CCK explains symptom severity in patients with DM with upper GI symptoms.

The **specific aims** of this study are to address the following hypotheses in 24 healthy subjects, 40 patients with DM and GI symptoms, and 40 patients with functional dyspepsia:

- 1) **A) Patients with DM and GI symptoms have increased intestinal chemosensitivity compared to controls and B) Intestinal chemosensitivity predicts severity of ongoing upper gastrointestinal symptoms independent of gastric emptying.** Intestinal chemosensitivity will be recorded by evaluating symptoms during duodenal lipid infusion (222 kcal, 222 ml) and placebo or the GLP-1 receptor antagonist exendin 9-39 over 2 hours; plasma hormones (i.e., glucose, CCK, GLP-1, PYY, C-peptide, will also be measured. Delivering nutrients into the duodenum will ensure that hormonal responses are not affected by gastric emptying disturbances. Day-to-day symptoms will be evaluated by the Nepean dyspepsia severity index and the GCSI. The relationship between daily symptoms and intestinal chemosensitivity will be assessed in a model which also incorporates gastric emptying and accommodation.

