- 2) **Intestinal chemosensitivity will be A) associated with higher plasma CCK and GLP-1 concentrations B) reduced by the GLP-1 antagonist exendin 9-39 and C) inversely associated with impaired abdominal vagal function.** This hypothesis will be evaluated by comparing intestinal chemosensitivity (a) with plasma CCK and GLP-1 concentrations (b) with and without exendin 9-39 and (c) in patients with and without and GI vagal dysfunction as assessed by the plasma pancreatic polypeptide response to sham feeding.
- 3) **A) Patients with DM and GI symptoms have abnormal epithelial tight junction proteins which predispose to increased epithelial permeability and increased small bowel permeability and B) These structural and functional markers of epithelial permeability are associated with intestinal chemosensitivity.** Intestinal permeability will be measured in vivo by two sugar urine excretion after oral ingestion. Biopsies from the distal second or third portion of the duodenum will be obtained endoscopically, to measure various markers of epithelial structure and function.

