3.5 Data Analysis

Chemosensitivity will be measured using a 100mmVAS anchored at each end (left end:No symptoms, right end: Severe symptoms). The distribution of this measure will be checked for its approximation to a gaussian distribution. An analysis to provide preliminary data for a new grant submission will be examined after approximately 15 subjects (5 DM, 10 controls) have completed the studies, but there is no intention of stopping the study based on the preliminary results. We anticipate conducting this analysis in July 2014 or thereafter.

Question	Summary Parameter	Statistical analysis
Sensation (symptoms) during enteral infusion (Aim 1)	VAS score	i) compare VAS scores in response to lipid infusion + exendin vs. lipid infusion + placebo separately for each group using a 2-sample t-test or Wilcoxon rank sum test ii) compare the delta VAS scores (exendin – placebo) to assess the association with subject status (FD,DM, and controls) using an ANOVA model (adjusting for covariates, eg, type of DM) or Kruskal-Wallis test.
Relationship between intestinal chemosensitivity and severity of ongoing upper GI symptoms	Mean symptom score and QoL defined by the Nepean dyspepsia index and GCSI diary	Multiple linear regression with the dependent variable = mean symptom score, and separately the QoL score (possibly after rank transformation). Potential predictor variables = VAS score during enteral lipid + placebo infusion, gastric emptying, age, gender, BMI
Relationship between sensation and plasma hormones during lipid infusion (Aim 2)	Using the VAS score from the enteral infusions and for hormones, the AUC values	Spearman correlations between the VAS score and the AUC values for the various hormones, overall and separately by group (FD,DM, controls)
Small intestinal tight junction proteins,	Protein expression, lactulose:mannitol	Assess the associations between permeability and protein expression, vs. the VAS score, based on Spearman

permeability, intestinal chemosensitivity	ratio, VAS score	correlations.
---	------------------	---------------

The sample size estimate is based on our previous study which evaluated intestinal chemosensitivity in functional dyspepsia in which the proportions with severe symptoms were assessed. [In the current proposal, symptoms during lipid infusion will be evaluated on a continuous VAS scale, likely providing the ability to detect smaller effect sizes]. The effect of lipid plus

Group	Proportions (%) with severe symptoms			

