	exendin+lipid vs. placebo+lipid	Controls vs. FD (exendin+lipid)	Controls vs. DM (exendin+lipid)	FD vs. DM (exendin+lipid)
Controls(n=12 vs n=12)	10% vs. 68%	10% vs. 60%	10% vs. 60%	30% vs. 73%
functional dyspepsia (n=20 vs. 20)	10% vs. 50%			
DM (n=20 vs. 20)	10% vs. 50%			

placebo vs. lipid plus exendin in response to enteral infusion can be based on a comparison of the proportions with severe symptoms using a two sample t-test. The association of group status with response to lipid plus exendin can also be assessed using a two-sample t-test for proportions. There is ~80% power (alpha =0.05, 2-sided) to detect the specified differences listed in the table below.

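### Aim 1A (DM more chemosensitive than controls) has no named test of symptom level, and the only between-group level contrast that is named and powered is under exendin, not lipid + placebo

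*Combined protocol and SAP*

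**What the plan says.** Section 1 (Specific Aims) gives Aim 1A as "Patients with DM and GI symptoms have increased intestinal chemosensitivity compared to controls". Aim 2B states that chemosensitivity will be "reduced by the GLP-1 antagonist exendin 9-39".

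The Aim 1 row of the table in section 3.5 lists two analyses:

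- Item i: "compare VAS scores in response to lipid infusion + exendin vs. lipid infusion + placebo separately for each group".
- Item ii takes the exendin-minus-placebo difference in VAS and uses it "to assess the association with subject status (FD,DM, and controls) using an ANOVA model", or a Kruskal-Wallis test.

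The next row, for Aim 1B, regresses daily symptoms on chemosensitivity: "Potential predictor variables = VAS score during enteral lipid + placebo infusion, gastric emptying, age, gender, BMI". The remaining rows are Spearman correlations.

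The sample-size text, also in section 3.5, adds: "The association of group status with response to lipid plus exendin can also be assessed using a two-sample t-test for proportions". The power table has one column for exendin vs placebo within each group and three between-group columns (controls vs FD, controls vs DM, FD vs DM). Each of those three is headed as exendin + lipid. The claim attached to the table is: "There is ~80% power (alpha =0.05, 2-sided) to detect the specified differences listed in the table below".

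**The concern.** Aim 1A is about the level of symptoms in DM compared with controls. Item i contains no comparison of groups. Item ii does compare groups, but on the drug effect. Each subject receives only one infusion, so item ii amounts to a group-by-arm interaction. If DM patients score higher than controls by the same amount in both arms, its expected value is zero.

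That leaves the contrast in the sample-size text, which is made while the GLP-1 receptor is blocked. The abstract's overall hypothesis names GLP-1 as part of the explanation for symptoms. If GLP-1 drives part of the DM-control difference, blocking it shrinks the quantity that Aim 1A is about.

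There are two ways this can go wrong. If the team uses the contrast that the sample-size text names, Aim 1A may be reported as negative although DM patients are more sensitive to lipid. If the team does not feel bound by that text, the choice between placebo-arm, exendin-arm and pooled comparisons is made after the data are seen.

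**Working it through.** **Inputs from the documents.** Section 3.5: two-sided alpha 0.05; 12 controls and 20 DM per arm; 10% vs 60% with severe symptoms for controls vs DM; VAS as the chemosensitivity measure, with no SD given. Abstract: 1:1 randomization within all three groups. (Section 3.3 item v lists only FD and DM as randomized; the power table's 12 vs 12 for controls agrees with the abstract.)

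**Step 1: the plan's own power figures.** Power by exact enumeration of the two binomial distributions:

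| Cell | n | t-test on 0/1 data | Fisher |
|---|---|---|---|
| Controls, 10% vs 68% | 12/12 | 0.90 | 0.79 |
| FD or DM, 10% vs 50% | 20/20 | 0.84 | 0.74 |
| Controls vs FD or DM, 10% vs 60% | 12/20 | 0.85 | 0.80 |
| FD vs DM, 30% vs 73% | 20/20 | 0.78 | 0.68 |

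About 80% is reasonable cell by cell. Read in heading order, the DM rate on exendin is 10% in the first column, 60% in the controls-vs-DM column and 73% in the FD-vs-DM column. The cells therefore make sense only as separate detectable differences, which the table does not say.

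**Step 2: detectable difference on the VAS, one arm, 12 vs 20.** The standard error in SD units is √(1/12 + 1/20) = 0.365. The normal approximation gives (1.96 + 0.84) × 0.365 = 1.02 SD. The noncentral t with 30 df gives 1.057 SD. This holds for either arm, because allocation is 1:1.

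**Step 3: what the planned tests see.** Let the DM-control difference be d = 1.057 SD on lipid + placebo, and let exendin leave a fraction r of it. The documents give no value for r, so the range is an assumption.

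- Exendin-arm contrast: effect r·d, SE 0.365, 30 df.
- Item ii as a DM-vs-control contrast: effect (1 − r)·d, SE √(2/12 + 2/20) = 0.516, df = 64 − 4 = 60.
- Group effect adjusted for arm, all 24 controls and 40 DM: effect (1 + r)/2·d, SE √(1/24 + 1/40) = 0.258, df = 64 − 3 = 61. Its detectable difference at 80% power is 0.735 SD.

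| r | Placebo-arm test (not in plan) | Exendin-arm contrast | Item ii | Arm-adjusted (not in plan) |
|---|---|---|---|---|
| 1 | 80% | 80% | 5% | 98% |
| 0.75 | 80% | 56% | 8% | 94% |
| 0.5 | 80% | 29% | 17% | 86% |
| 0.25 | 80% | 11% | 33% | 71% |

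At r = 1 item ii rejects only at its 5% alpha, which is the blindness to an equal shift in both arms.

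**Step 4: the placebo arm as proportions, 12 vs 20.** Power (Fisher to t-test) is 80–85% for 10% vs 60%, 61–67% for 10% vs 50%, and 51–61% for 20% vs 60%. The last two pairs are illustrations. The documents do not label any figure as an expected control rate on lipid + placebo, so the smallest DM rate detectable at 80% power is shown over an assumed range:

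| Control rate | Smallest DM rate (t-test to Fisher) |
|---|---|
| 5% | 49–51% |
| 10% | 57–61% |
| 20% | 69–74% |
| 30% | 79–82% |

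**The case against.** The strongest reply is that the exendin headings are a slip for placebo. The sample size is said to come from an earlier functional dyspepsia study, and the preliminary data shown in section 2 compare patients with controls during lipid infusion with no mention of exendin. This is plausible, and the sample size and the power at 10% vs 60% would carry over unchanged. But the running text names the exendin arm as well as the headings do. A 10% control rate on placebo would also sit beside 68% for controls in the first column unless the cells are labelled as detectable differences. If it is a slip, correcting it is the change requested here, and the Aim 1 row would still lack the test.

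Second, the loss of power depends on r. Aim 2B predicts that exendin lowers chemosensitivity, not that it narrows the gap between groups. The hypothesis as worded in section 1 names CCK rather than GLP-1. An equal reduction in both groups leaves 80% power, and a larger reduction in controls would widen the contrast. This stands: the attenuation is a risk, not a prediction. The missing test does not depend on it. The t-test for proportions in the sample-size text is also on a different scale from the VAS series in step 3, which shows the pattern rather than the power of that exact test.

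Third, a group-by-arm ANOVA would contain a group term. True, but the plan sets the drug-effect difference as the outcome and does not name or power a group effect on level. Finally, Aim 1 records symptoms under placebo or exendin, so an exendin-arm contrast is legitimate evidence on Aim 1A. It should not be the only one.

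**Conclusion.** The concern holds. No row of the analysis table tests DM vs controls on symptom level, and the only level contrast named or powered is in the arm where the plan expects chemosensitivity to be reduced. The plan's power arithmetic is not at fault.

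The omission itself is certain from the text. The size of the loss is conditional: for a 1.06 SD difference on lipid + placebo, power in the exendin arm is 80% if exendin leaves the difference intact and falls to 56%, 29% or 11% if it leaves 75%, 50% or 25%. These figures assume equal SDs, approximately Gaussian VAS scores, and controls randomized 1:1 as the abstract states. This should be fixed before analysis; it does not call the sample size or the design into question.

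**What to change.** 1. Add to the Aim 1 row a comparison of DM with controls on VAS during lipid + placebo, adjusted for age and gender (the factors used for frequency matching in section 3.2), rank-based if the distribution is not Gaussian. Name it as the Aim 1A test. List FD vs controls in the same arm as a separate contrast, since Aim 1A concerns DM only.
2. Restate the between-group power columns for lipid + placebo. Label every cell as a difference detectable at about 80% power, and give the VAS equivalent (1.06 SD at 12 vs 20).
3. Keep the exendin-arm contrast as supporting. A group effect adjusted for arm, using all 24 controls and 40 DM, could be a second supporting analysis. It detects 0.735 SD but averages over blocked and unblocked receptor states, so it answers a slightly different question.
4. Make section 3.3 item v agree with the abstract on whether controls are randomized.

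The cost is one analysis line and relabelled columns, on data already being collected, with no extra subjects. The downside is that the named test uses half the subjects and the plan must show a detectable difference of about 1 SD. That limit is already in the design.

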3.6 Potential Pitfalls

To reduce the likelihood of patient intolerance, a smaller diameter tube will be used for enteral nutrient infusion. Only lipid and not carbohydrate infusions will be given; hence the duration of this study is shorter and hyperglycemia during nutrient infusion is less likely.

4 HUMAN SUBJECTS

Description: Studies will be conducted over 3 days. Subjects will be remunerated \$ 600. A screening assessment will be performed to ensure subjects fulfill entry criteria. Subjects will fast overnight prior to study days. Study procedures will be performed using established techniques by experienced technicians in our programs.

Research Materials: Blood samples (hormones, glucose, extract DNA and RNA) and stool samples will be obtained for this study.

Population and Recruitment of Subjects: Healthy subjects will be recruited from the community and patients with DM and dyspepsia will be recruited from the clinical practice and to patients who have provided research authorization. The Institutional Review Board will approve all recruitment materials. After discussing the study procedure and its risks, informed consent will be obtained, before study procedures. No children or prisoners will be recruited.

Potential Risks: Blood sampling. Blood samples are collected by venipuncture for this study. Assays for measuring blood glucose and plasma hormone will require 19ml blood at each of 18 time points during the enteral infusion study. The total blood drawn is 408 ml. Bruising can occur with venipuncture, as can fainting, etc. Risk Monitoring/Risk Reduction: The samples are collected using aseptic technique in the venipuncture area of the Clinical Research Unit where facilities are available should untoward reactions (fainting, etc.) occur. Given the aseptic nature of the sample collection and the small risk of bruising, the monitoring plan is focused on advising volunteers to call the co-investigators (physician) should they have unusual pain or discomfort from the venipuncture site.

Enteral tube placement This will require exposure to radiation and may be associated with discomfort. The risk of perforation with a soft-tipped feeding tube is very low. Risk Monitoring / Risk Reduction: The radiation safety committee will review all projected exposure to radiation prior to approval of the protocol by the IRB. The small bore soft-tipped feeding tube will be positioned by trained personnel under fluoroscopic guidance in the CRU. Subjects will be closely monitored for tolerance. **Enteral nutrition.** This may be associated with nausea and abdominal cramping symptoms. Risk Monitoring/Risk Reduction: Subjects will fast overnight prior to the lipid infusion. To minimize the effect on blood glucose, lipid instead of glucose infusion is being administered. They will be closely monitored by trained personnel. **Exendin 9-39 infusion.** The effects of exendin infusion on postprandial blood glucose concentrations is modest. For example, in 1 study blood glucose concentrations after a duodenal meal were on average only 6 mg/dl higher in healthy subjects and 19 mg/dl higher in T2DM for exendin 9-39 versus saline⁴⁷. Risk Monitoring / Risk Reduction: Blood glucose concentrations will be monitored regularly and insulin will be administered if necessary. **Gastric emptying.** Gastric emptying and small intestinal transit will be measured by scintigraphy. This will require exposure to radiation. Risk Monitoring / Risk Reduction: The radiation safety committee will review all projected exposure to radiation prior to approval of the protocol by the IRB. Pregnancy tests will be checked within 48 hours prior to each study day. Vital signs will be recorded before the study.

Dosimetry and Organ Exposure in mrad (see attached under APPENDIX)

In view of the radiation exposure, all females of childbearing age will be required to have a negative urine pregnancy test within 1 week of this study.

Protection: The key personnel in this application have completed the required education on the protection of human research participants. The institution has established a formal program entitled the Mayo Investigator Training Program or MITP. The MITP is a web based educational course designed to provide all personnel involved in human subject research with training about human subject protection. All Mayo personnel engaged in human subject research are required to complete the course.

Data Safety and Monitoring Plan. The ultimate goal of this application is to further our understanding of GI symptoms in patients with dyspepsia and diabetes. The DSMP utilized will adhere to the protocol approved by the Mayo Clinic IRB. We propose the following plan: -

Data quality and management: The principal investigator will review all data collection forms on a three-monthly basis for completeness and accuracy of the data as well as protocol compliance.

Adverse events grading: The common grading scale listed below will be used to grade AEs:

0 No adverse event or within normal limits or not clinical significant

1 Mild AE, did not require treatment
 2 Moderate AE, resolved with treatment
 3 Severe AE, resulted in inability to carry on normal activities and required professional medical attention
 4 Life threatening or disabling AE
 5 Fatal AE

Attribution scale: An adverse event includes both, an expected side effect that is of a serious nature, or an unexpected side effect/ event regardless of severity. All events will be graded as to their attribution (unrelated to protocol, or possibly, probably, or definitely related to protocol). Any event that is reported to either the principal investigator or his designated research associates by the subject or medical staff caring for the subject and which meets the criteria will be documented as such.

Data Monitoring. The majority of data generated from these protocols will be from analyses performed in our laboratory or the immunochemical core laboratory. Standard quality control procedures are in place for each assay. The frequency of data review for this study differs according to the type of data and can be summarized in the following table:

Data type	Frequency of review
Subject accrual (adherence to protocol regarding demographics, inclusion/exclusion)	Weekly
Adverse event/safety rates (injuries)	Weekly
Annual report	Yearly for IRB

Informed Consent. Written informed consent will be obtained from all individuals who participate in the study. The principal investigator or his co-investigators meet with each participant, review the consent form in detail and confirm the subjects understanding of the study. They answer all questions posed by the participants and when convinced that the subject verbally demonstrates understanding of the protocol obtains a signed consent. Only designated staff are authorized to obtain informed consent.

Benefits: This study exposes subjects to risks detailed above. However, it will advance our knowledge of the mechanisms of GI sensorimotor dysfunctions in patients with DM.

5 SAFETY AND ADVERSE EVENTS

5.1 Definitions

Unanticipated Problems Involving Risk to Subjects or Others (UPIRTSO)

Any unanticipated problem or adverse event that meets the following three criteria:

- **Serious:** Serious problems or events that results in significant harm, (which may be physical, psychological, financial, social, economic, or legal) or increased risk for the subject or others (including individuals who are not research subjects). These include: (1) death; (2) life threatening adverse experience; (3) hospitalization - inpatient, new, or prolonged; (4) disability/incapacity - persistent or significant; (5) birth defect/anomaly; (6) breach of

confidentiality and (7) other problems, events, or new information (i.e. publications, DSMB reports, interim findings, product labeling change) that in the opinion of the local investigator may adversely affect the rights, safety, or welfare of the subjects or others, or substantially compromise the research data, **AND**

- **Unanticipated:** (i.e. unexpected) problems or events are those that are not already described as potential risks in the protocol, consent document, not listed in the Investigator's Brochure, or not part of an underlying disease. A problem or event is "unanticipated" when it was unforeseeable at the time of its occurrence. A problem or event is "unanticipated" when it occurs at an increased frequency or at an increased severity than expected, **AND**
- **Related:** A problem or event is "related" if it is possibly related to the research procedures.

Adverse Event

An untoward or undesirable experience associated with the use of a medical product (i.e. drug, device, biologic) in a patient or research subject.

Serious Adverse Event

Adverse events are classified as serious or non-serious. Serious problems/events can be well defined and include;

- death
- life threatening adverse experience
- hospitalization
- inpatient, new, or prolonged; disability/incapacity
- persistent or significant birth defect/anomaly

and/or per protocol may be problems/events that in the opinion of the sponsor-investigator may have adversely affected the rights, safety, or welfare of the subjects or others, or substantially compromised the research data.

Other important medical events are those that may not be immediately life threatening, but are clearly of major clinical significance. They may jeopardize the subject, and may require intervention to prevent one of the other serious outcomes noted above. For example, drug overdose or abuse, a seizure that did not result in in-patient hospitalization or intensive treatment of bronchospasm in an emergency department would typically be considered serious.

All adverse events that do not meet any of the criteria for serious, should be regarded as **non-serious adverse events**.

Withdrawal criteria

- Inability to place nasoduodenal feeding tube
- Inability to obtain intravenous access
- Severe abdominal discomfort, nausea or vomiting during enteral nutrient infusion
- Severe hyperglycemia (> 400 mg/dl) unresponsive to insulin therapy

Adverse Event Reporting Period

Example

For this study, the study treatment follow-up period is defined as 1 days following the last administration of study treatment. The study period during which adverse events must be reported is normally defined as the period from the initiation of any study procedures to the end of the study treatment follow-up.

Preexisting Condition

A preexisting condition is one that is present at the start of the study. A preexisting condition should be recorded as an adverse event if the frequency, intensity, or the character of the condition worsens during the study period.

General Physical Examination Findings

At screening, any clinically significant abnormality should be recorded as a preexisting condition.

At the end of the study, any new clinically significant findings/abnormalities that meet the definition of an adverse event must also be recorded and documented as an adverse event.

Post-study Adverse Event

All unresolved adverse events should be followed by the sponsor-investigator until the events are resolved, the subject is lost to follow-up, or the adverse event is otherwise explained. At the last scheduled visit, the sponsor-investigator should instruct each subject to report, to the sponsor-investigator, any subsequent event(s) that the subject, or the subject's personal physician, believes might reasonably be related to participation in this study.

Hospitalization, Prolonged Hospitalization or Surgery

Any adverse event that results in hospitalization or prolonged hospitalization should be documented and reported as a serious adverse event unless specifically instructed otherwise in this protocol. Any condition responsible for surgery should be documented as an adverse event if the condition meets the criteria for an adverse event.

Neither the condition, hospitalization, prolonged hospitalization, nor surgery are reported as an adverse event in the following circumstances:

- Hospitalization or diagnostic or elective surgical procedures for a preexisting condition. Surgery should not be reported as an outcome of an adverse event if the purpose of the surgery was elective or diagnostic and the outcome was uneventful.
- Hospitalization or prolonged hospitalization for therapy of the target disease of the study (e.g., diabetes mellitus), unless it is a worsening or increase in frequency of hospital admissions as judged by the clinical investigator.

